#### 4.2.3 Washout Period

The minimum washout period between each investigational medicinal product (IMP) administration is set to 7 days in accordance with the WHO Guidance. It is expected that for logistic reasons a washout period of 7 days is convenient. From a scientific point of view a shorter

period could be envisaged as the mean half-life of rac-PZQ is 2.5 hours while the half-life of the main trans-OH-rac-PZQ metabolite is approximately 4.5 hours (Geomean; min-max 2.8 to 6.3 hours; data on file). In addition, for individual cases a longer washout period could be allowed.

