### 8.2.3 Electrocardiograms

- Single 12-lead ECG will be obtained as outlined in the SoA using an ECG machine that automatically calculates the heart rate and measures PR, QRS, QT, and QTc intervals.

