### 8.2.4 Clinical Safety Laboratory Assessments

- Blood and urine samples will be collected for the clinical laboratory tests listed in [Appendix 5](#) at the time points listed in the SoA. All samples should be clearly identified.
- Additional tests may be performed at any time during the study, as determined necessary by the Investigator or required by local regulations.
- The tests will be performed by the Nuvisan laboratory. Reference ranges of the laboratory parameters for the Nuvisan laboratory are provided in [Appendix 8](#).
- The Sponsor must receive a list of the local laboratory normal ranges before shipment of study intervention(s). Any changes to the ranges during the study must be forwarded to Sponsor.
- The Investigator must review each laboratory report, document this review, and record any clinically relevant changes occurring during the study in the AE section of the CRF. The laboratory reports must be filed with the source documents.
- A Laboratory Manual will be prepared which contains the following information: sampling methods (e.g. whole blood, plasma, serum, urine), processing and storage of samples through to the analysis, and any special analysis methods.

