Repeated and unscheduled measurements will be included in the listings, but not used for statistical analysis or summary tables, unless the repeated measurement was performed due to unreliable values/technical reasons, e.g., clotted samples.

In this phase 1 PK study, missing observations will be assumed to be missing completely at random (MCAR). No action will be taken to handle missing data. A participant who withdraws prior to the last planned observation in a trial period will be included in the analyses up to the time of discontinuation.

The following treatment labels will be used:

Treatment Tx: x. administration of coated Cesol tablet, 2 tablets of praziquantel 600 mg per period,

Treatment Rx: x. administration of Biltricide[®], 2 tablets of praziquantel 600 mg per period

where x=1 or x=2 defines the first and second administration of test or reference product, respectively. These labels will be used in listings and summaries by first treatment and second treatment.

Treatment Total T: coated Cesol tablet, 2 tablets of praziquantel 600 mg per period,

Treatment Total R: Biltricide[®], 2 tablets of praziquantel 600 mg per period,

whereby these treatment labels will be used in summaries by total treatment.

10 Trial Participants

The subsections in this section include specifications for reporting participant disposition and treatment/trial discontinuations. Additionally, procedures for reporting protocol deviations are provided.

Considering the study objectives, it is planned to enroll 36 participants in the study to ensure inclusion of at least 32 evaluable participants for the treatment comparisons.

The participants will be randomized to one of the two treatment sequences: T1-R1-T2-R2 or R1-T1-R2-T2, where T is Test product and R is Reference product, with a washout period of at least 1 week in between.

	Period 1		Period 2		Period 3		Period 4
Sequence 1 (18 participants)	Test 1	Washout at least 7 days	Reference 1	Washout at least 7 days	Test 2	Washout at least 7 days	Reference 2
Sequence 2 (18 participants)	Reference 1		Test 1		Reference 2		Test 2

Test = coated Cesol tablet, 2 tablets of praziquantel 600 mg;
Reference = Biltricide, 2 tablets of praziquantel 600 mg.

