15.5 ECG Evaluation

ECG data will be listed by participant and time-point and summarized by absolute values and changes-from-baseline (period-baseline) by treatment T1, T2, R1 and R2 using descriptive statistics. Descriptive statistics tables will start at baseline. Clinically significant ECG findings for individual participants will be listed and summarized.

The time intervals (PR, QRS, RR, QT and corrected QT intervals [based on Fridericia's formula, QTcF]) will be summarized descriptively by treatment.

The Fridericia's Correction (QTcF) is derived as follows:

$$\text{Fridericia's Correction (QTcF)} \quad QTc_f = \frac{QT}{\sqrt[3]{RR}}$$

where: RR = RR-interval measured in seconds.

Observed QTcF values will be categorized according to their absolute values into the categories

- ≤ 430 ms,
- > 430 and ≤ 450 ms,
- > 450 and ≤ 480 ms,
- > 480 and ≤ 500 ms, and
- > 500 ms,

and categorized according to their absolute change from period baseline into the categories

- ≤ 30 ms,
- > 30 and ≤ 60 ms, and
- > 60 ms.

The number and percentage of participants by these categories at any post-dose assessment will be tabulated by treatment T1, T2, R1 and R2. All ECG measurements and changes from period baseline will be listed, with abnormalities (as reported of the investigator on the ECG eCRF page) indicated.

Investigator reported interpretation results will also be tabulated by treatment T1, T2, R1 and R2 using the number and percentage of participants for each interpretation category (Normal, Abnormal Not Clinically Significant [NCS], Abnormal Clinically Significant [CS]).

16 Analyses of Other Endpoints

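### SAP Section 9 keeps unscheduled ECGs out of summary tables, Section 15.5 counts QTcF categories at any post-dose assessment, and the SAP does not say which rule prevails

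*SAP*

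**What the plan says.** SAP Section 9 (General Specifications for Data Analyses) sets a rule for all data types: "Repeated and unscheduled measurements will be included in the listings, but not used for statistical analysis or summary tables". Its one exception reads "unless the repeated measurement was performed due to unreliable values/technical reasons, e.g., clotted samples". Nothing is said about recordings prompted by symptoms or ordered for safety.

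SAP Section 15.5 (ECG Evaluation) defines QTcF categories by absolute value (top category above 500 ms) and by change from period baseline (top category above 60 ms). It then says: "The number and percentage of participants by these categories at any post-dose assessment will be tabulated by treatment T1, T2, R1 and R2". It adds: "Clinically significant ECG findings for individual participants will be listed and summarized". Investigator interpretations are tabulated by the same four treatment labels. On listings it says: "All ECG measurements and changes from period baseline will be listed, with abnormalities". None of these sentences mentions unscheduled ECGs.

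Protocol Section 8.2.3 says: "Single 12-lead ECG will be obtained as outlined in the SoA". The Schedule of Activities (Protocol Section 1.3) marks ECGs at Screening, at -1 h and 24 h of each period, and at the End of Treatment/Safety Follow-up visit on Day 27 (± 3 days).

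**The concern.** Categorical QTcF tables exist to show outlying values. A general rule that keeps unscheduled readings out of summaries suits descriptive statistics by time point, where each participant should contribute once per time point. It suits a worst-case table poorly, because an extra ECG is often taken when something is suspected.

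In this trial no ECG is scheduled between dosing and 24 h, so an ECG taken while drug is present is unscheduled by construction. If Section 9 governs, the category tables could show no outlier while the ECG listing shows one. ECG parameters are a named secondary safety endpoint, and the benefit-risk report in Protocol Appendix 7 lists cardiac arrhythmias as an important identified risk. The clinical study report should therefore not contain that mismatch.

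**Working it through.** The plan gives no figure on this point to reproduce. The check sets the two rules against the ECG schedule and asks what each reading leaves in the tables.

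**Scheduled ECGs per participant** (Protocol Section 1.3)
- Screening 1, plus 4 periods × 2 (-1 h and 24 h), plus follow-up 1: 1 + 8 + 1 = 10.
- Post-dose: 4 at 24 h and 1 at follow-up. Between 0 h and 24 h: none.
- With the nominal 7-day washout the last dose is on Day 22, so follow-up falls 27 − 22 = 5 days after it (range 2 to 8 days).

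**Drug remaining at 24 h.** Protocol Section 4.2.3 says "the mean half-life of rac-PZQ is 2.5 hours" and gives about 4.5 h (2.8 to 6.3 h) for the main metabolite. Assuming first-order decline, the fraction remaining is 0.5^(24 / half-life).

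| Analyte | Half-life (h) | Half-lives in 24 h | Remaining at 24 h |
|---|---|---|---|
| rac-PZQ | 2.5 | 9.6 | 0.13% |
| Main metabolite, geometric mean | 4.5 | 5.3 | 2.5% |
| Main metabolite, shortest | 2.8 | 8.6 | 0.3% |
| Main metabolite, longest | 6.3 | 3.8 | 7.1% |

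This simple decay starts the clock at dosing and ignores absorption time, so the fractions are approximate.

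**What each reading leaves in the tables**
- *Section 9 prevails.* In periods 1 to 3, any post-dose assessment reduces to the single 24 h ECG. Period 4 gains at most the follow-up ECG. No recording from the first 24 h can enter.
- *Section 15.5 prevails.* Unscheduled ECGs count, but the SAP does not say how several recordings in one period become one category per participant.

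**Effect of one participant.** Section 9 bases percentages by T1, T2, R1 and R2 on the number dosed with that treatment. With all 36 dosed, one participant is 1/36 = 2.8 percentage points; with 32 it is 1/32 = 3.1. The documents give no expected number of unscheduled ECGs, so the total effect cannot be computed.

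**The case against.** A reader might infer that unscheduled ECGs are definitely barred from these tables and that a cardiac signal would be lost. The documents do not support that, for four reasons.

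- **Section 15.5 may already override Section 9.** It is the more specific section. With one scheduled post-dose ECG in each of periods 1 to 3, the word any means little unless unscheduled ECGs count. Against this, Section 9 attaches an override clause to its definition of baseline and none to its rule on unscheduled data. Neither reading is secured by the text.
- **The data are not lost.** All ECG measurements are listed. Under Protocol Appendix 4, an abnormal ECG finding is reported as an adverse event if it comes with signs or symptoms, leads to discontinuation or is judged medically important. It would then reach the TEAE tables in SAP Section 15.1. Palpitations with a QTcF above 500 ms would be captured that way. This stands, although TEAE tables do not supply QTcF category counts, and a finding judged not to meet those criteria would appear only in the listing.
- **Unscheduled ECGs may never occur.** The protocol sets no symptom-driven ECG procedure. The sentence "Additional tests may be performed at any time during the study, as determined necessary by the Investigator" belongs to the laboratory section (Protocol Section 8.2.4) and is not an ECG provision.
- **The risk background is limited.** The same benefit-risk report finds little evidence linking praziquantel to arrhythmia and cites two non-serious, unconfirmed reports with alternative explanations. The risk it names is arrhythmia, not QTc prolongation.

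There is also a fair argument for scheduled-only tables. The study is open-label, and ECGs ordered at discretion may be taken unevenly under test and reference. That is a real, small cost of counting them.

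**Conclusion.** The point holds as an unresolved conflict within the SAP; it does not show an omission. Sections 9 and 15.5 give different answers on whether an unscheduled ECG enters the QTcF category, clinically significant finding and interpretation tables. The schedule makes the answer matter: if Section 9 prevails, any ECG taken during exposure is left out, and the tables rest on recordings about 9.6 rac-PZQ half-lives after dosing or later.

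The size is minor: 2.8 percentage points per affected participant in a column of 36, and nothing if no unscheduled ECG is taken. The tables are descriptive, and the bioequivalence analysis is unaffected. The conclusion assumes the half-lives in Protocol Section 4.2.3 with first-order decline. It does not depend on the exact residual, since no ECG is scheduled in the first 24 h in any case. The placement of ECGs at 24 h is a design feature that this point does not ask to change.

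**What to change.** Add to SAP Section 15.5, before database lock: *As an exception to Section 9, the QTcF category tables and the tables of clinically significant findings and investigator interpretation use the worst valid post-dose value in the period, scheduled or unscheduled. Recordings replaced because of unreliable values or technical reasons are not used. A footnote identifies participants counted only through an unscheduled ECG.* Keep descriptive statistics by time point on scheduled ECGs.

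The technical-repeat clause is needed because a plain worst-of-all rule could pick up a faulty tracing that was later repeated. The footnote makes any uneven ordering of ECGs between treatments visible.

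The cost is a few lines of SAP text and one programming flag. No new assessment is needed. Protocol Section 9.4.2 commits only to ECG listings and to descriptive summaries by treatment and time point, which stay as they are, so no protocol amendment is needed for this change.

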8.1 Definition of Protocol Deviations and Analysis Sets

Important protocol deviations are protocol deviations that might significantly affect the completeness, accuracy, and/or reliability of the study data or that might significantly affect a participant's rights, safety, or well-being.

The following deviations will be identified and confirmed prior to or at the Data Review Meeting at the latest.

Important protocol deviations include

- Deviations from the inclusion and exclusion criteria
- Concomitant medication violations (see Section 6.5.2 of the protocol)
- Use of prohibited medicines (see Section 6.5.3 of the protocol)
- Participants who receive incorrect treatment or dose
- Sample processing errors that may lead to inaccurate bioanalytical results
- Vomiting or diarrhea following oral dosing (these instances will be discussed on a case-by-case basis)
- Deviation from Good Clinical Practice

- Non-compliance to study procedures or deviations from study procedures likely to affect the primary endpoints (e.g. participant develops withdrawal criteria whilst in the study but is not withdrawn)
- Deviation from study medication compliance in terms of medical conditions and/or AEs that may have interfered with drug disposition or with respect to factors likely to affect the primary endpoints

All important protocol deviations will be documented in Clinical Data Interchange Standard Consortium (CDISC) Study Data Tabulation Model (SDTM) datasets whether identified through sites monitoring or medical review.

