CV%, GeoCV%:	1 decimal place
Ratio of GeoMean (in %) and 95% CI	2 decimal places

To ensure a reliable estimate of the extent of exposure, AUC_{extra} should be less than or equal to 20%. If AUC_{extra} is greater than 20%, all parameters derived using λ_z (i.e. λ_z , $t_{1/2}$, $AUC_{0-\infty}$, AUC_{extra} , V_z/f , CL/F) will be listed, but set to missing for the calculation of descriptive statistics.

All statistical analyses and descriptive summaries of pharmacokinetic data will be performed on the PK Analysis Set. All available data will be listed. Data of participants not in the PK analysis set or invalid data will be flagged accordingly. Any flags will be included in SDTM and ADaM, respectively.

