16.1.1 Planned Analyses of PK Parameter Data

The following PK parameter tables will be produced:

- Summary of PK parameters by treatment T1, T2, R1 and R2 of all analytes.

The following listing will be produced:

- Individual PK parameters listed by treatment T1, T2, R1, R2. Excluded PK parameters will be flagged.

The following figures will be produced for PK parameters:

- Boxplots for the C_{\max} and AUC_{0-t} by treatment T1, T2, R1, R2 of all analytes.

The analysis of the primary endpoints AUC_{0-t} and C_{\max} of rac-PZQ will be performed using the PK population. The analysis of the secondary endpoints AUC_{0-t} and C_{\max} of R-(-)-PZQ and S-(+)-PZQ will use a similar approach.

For the analysis of AUC_{0-t} and C_{\max} , a reference-scaled BE approach will be applied as follows:

The within-subject variability of the reference product will be calculated from a linear model fitted to the log-transformed PK parameters C_{\max} and AUC_{0-t} , obtained under reference treatment only, with sequence, subject within sequence, period included as fixed effects, described in Section 3.4 of Question 8 in [EMA/618604/2008 Rev. 13: Questions & Answers](#): positions on specific questions addressed to the Pharmacokinetics Working Party (PKWP). In this analysis, only participants with evaluable data from both administrations of the reference product will be included. If the within-subject coefficient of variation for the reference treatment ($CV_{WR} \leq 30\%$ for C_{\max} or AUC_{0-t} (i.e. the within-subject CV for the reference drug is $\leq 30\%$), then the common acceptance range (80.00% to 125.00%) for BE will apply for the respective PK parameter. For $30\% < CV_{WR} \leq 50\%$ the acceptance interval will be widened according to $[L, U] = \exp(\mp k s_{WR})$, where U is the upper limit of the acceptance range, L is the lower limit of the acceptance range, k is the regulatory constant set to 0.760 and s_{WR} is the intrasubject standard deviation of the log-transformed values of C_{\max} or AUC_{0-t} of the reference product, and $CV_{WR} = \sqrt{\exp(s_{WR}^2) - 1}$. s_{WR} will be calculated using the data under reference treatment only. For all values of CV_{WR} greater than 50% the acceptance range is fixed to [69.84% to 143.19%].

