An analysis of variance (ANOVA) with treatment, period, sequence and subject within sequence as fixed effects, will be fitted to log-transformed PK parameters AUC_{0-t} and C_{\max} according to Method A in Question 8 in [EMA/618604/2008 Rev. 13](#). Only participants with at least one valid PK parameter under both reference and test treatment will be included in this model. Least-squares mean differences between treatments will be derived on the log-scale together with 90% confidence intervals.

Estimates and confidence intervals will be back-transformed to the natural scale. Bioequivalence will be accepted if, firstly, the back-transformed 90% confidence intervals are included in the acceptance range, and, secondly, the geometric mean ratios are contained in the conventional acceptance range 80.00% to 125.00%.

The estimated within-subject variability CV_{WR} may be inflated in the presence of outliers. In order to exclude such inflation, sensitivity analyses will be performed. In these analyses, outliers will be identified using graphical methods by plotting the PK parameter after the first administration (R1) against the corresponding value after the second administration (R2), and/or statistical methods (such as identifying subjects whose studentized residuals fall outside the

interquartile range and/or outside the whiskers), and the acceptance range will be based on CV_{WR} calculated with outliers removed from the dataset.

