16.1.3 Estimation of Individual PK Parameters

The following non-compartmental PK parameters will be calculated from the individual plasma rac-PZQ, R-(-)-PZQ and S-(+)-PZQ concentration-time data using commercial software Phoenix[®]/WinNonlin[®] (Version 6.3 or higher) at PPD. C_{max} and AUC_{0-t} are the main parameters for further statistical analysis.

Symbol	Definition
AUC_{0-t}	The area under the concentration-time curve (AUC) from time zero (= dosing time) to the last sampling time (t_{last}) at which the concentration is at or above the lower limit of quantification. Calculated using the mixed log-linear trapezoidal rule (linear up, log down).

Symbol	Definition
$AUC_{0-\infty}$	The AUC from time zero (dosing time) extrapolated to infinity, based on the predicted value for the concentration at t_{last} , as estimated using the linear regression from λ_z determination. $AUC_{0-\infty} = AUC_{0-t} + C_{last\ pred} / \lambda_z$.
$AUC_{extra\%}$	The AUC from time t_{last} extrapolated to infinity given as percentage of $AUC_{0-\infty}$. $AUC_{extra\%} = (\text{extrapolated area}/AUC_{0-\infty}) * 100$. The predicted $AUC_{0-\infty}$ should be used.
CL/f	The apparent oral clearance. $CL/f = \text{Dose}_{p.o.} / AUC_{0-\infty}$. The predicted $AUC_{0-\infty}$ should be used.
C_{max}	Maximum observed concentration.
$t_{1/2}$	Apparent terminal half-life. $t_{1/2} = \ln(2) / \lambda_z$.
t_{lag}	The time prior to the first measurable (non zero) concentration.
t_{max}	The time to reach the maximum observed concentration collected during a dosing interval (i.e., 1 st occurrence in case of multiple/identical C_{max} values).
V_z/f	The apparent volume of distribution during the terminal phase following extravascular administration. $V_z/f = \text{Dose} / (AUC_{0-\infty} * \lambda_z)$ following single dose.
λ_z	Terminal first order (elimination) rate constant. Determined from the terminal slope of the log-transformed concentration curve using linear regression on terminal data points of the curve.

The following PK parameters will be calculated for diagnostic purposes and listed, but will not be summarized:

- First ($\lambda_{z\ low}$) and last ($\lambda_{z\ upp}$) time point of the time interval of the log-linear regression to determine λ_z .
- Number of data points (N_λ) included in the log-linear regression analysis to determine λ_z .
- Goodness of fit statistic (adjusted Rsq) for calculation of λ_z .

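### Could a withdrawal during sampling let a cut-off AUC0-t into the primary bioequivalence analysis?

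*SAP*

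**What the plan says.** SAP section 9 (General Specifications for Data Analyses) assumes that missing observations are missing completely at random and adds "No action will be taken to handle missing data". On early departure, its rule is that anyone "who withdraws prior to the last planned observation in a trial period will be included in the analyses up to the time of discontinuation". It makes no exception for derived PK parameters.

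SAP 16.1.3 defines AUC0-t as running "from time zero (= dosing time) to the last sampling time" with a concentration at or above the LLOQ. It sets no minimum sampling duration.

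SAP 16.1.1 controls entry to the two models that decide bioequivalence:
- For the ANOVA: "Only participants with at least one valid PK parameter under both reference and test treatment will be included in this model".
- For the reference within-subject variability: "only participants with evaluable data from both administrations of the reference product will be included".
- For single values left out: "Excluded PK parameters will be flagged".

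SAP 16.1 has a rule for extrapolated area above 20%, but it covers only parameters that depend on λz. These "will be listed, but set to missing for the calculation of descriptive statistics". AUC0-t is not among them.

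SAP 8.1 counts as important any "deviations from study procedures likely to affect the primary endpoints". SAP 8.2 removes participants with important events affecting PK and explains *evaluable* as nonmissing primary endpoints in each *completed* period. Protocol 9.3 places the final decision on exclusions in a data review meeting before database lock, held without knowledge of treatment allocation.

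**The concern.** If blood sampling stops at, say, 4 h because the participant leaves, AUC0-t can still be computed but covers only part of the profile. Read literally, section 9 keeps it. The words *valid* and *evaluable* have no written completeness criterion for a single period, and the extrapolation rule does not reach AUC0-t.

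A cut test value would lower the test/reference ratio and a cut reference value would raise it. A cut second reference value would also inflate CV_WR, which widens the acceptance range. An incomplete reference profile could then make the criterion easier to meet. Whether the value enters a primary analysis would rest on judgement, not on a stated rule.

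**Working it through.** **The plan's own figures.** Protocol 7.2 sets a 10% nonevaluable rate and at least 32 evaluable participants: 32/0.90 = 35.6, so 36, as stated. The widening cap at CV_WR 50% is exp(∓0.760 × √ln(1 + 0.5²)) = 69.84% to 143.19%, as stated in SAP 16.1.1.

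**Where a cut value can enter.** A period 1 withdrawal has data under one treatment only, so the ANOVA entry rule excludes it. Withdrawal during the first reference dose leaves no second one, so it cannot enter the CV_WR model. The exposure is therefore periods 2 to 4 for the ANOVA, and the second reference dose for CV_WR. If protocol 9.3 is read literally (nonmissing values in each study period, without *completed*), only period 4 remains.

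**How often.** The documents give no rate for withdrawal during sampling. Protocol 4.3 reports no withdrawals due to TEAEs among 32 healthy participants in an earlier four-way study of other formulations. The one-sided 95% upper bound is 1 − 0.05^(1/32) = 8.9% per participant, or 36 × 0.0894 = 3.2 participants. This overstates the exposure: it covers four whole periods at 40 to 60 mg/kg, against 12.6 to 21.8 mg/kg here, and only a stop within the 12 h sampling window matters. Protocol 4.1 confines participants until 24 h after dosing.

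**How much AUC is lost.** Inputs: half-life 2.5 h (protocol 4.2.3), the planned sampling times (protocol 8.5) and the linear-up/log-down rule. Assumptions not in the documents: a one-compartment model and tmax from 1.5 to 3.5 h.

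| Last sample | Share of AUC0–12h kept |
|---|---|
| 3 h | 25–47% |
| 4 h | 37–61% |
| 6 h | 60–80% |
| 8 h | 78–90% |
| 10 h | 91–97% |

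**Shift in the ratio.** With 16 participants per sequence, one cut value and no later data from that participant, the cut log value has a least-squares weight w in the treatment difference of 0.0159 (period 2), 0.0105 (period 3) or 0.0156 (period 4). For share f kept, the shift is exp(w × ln f) − 1, with the sign reversed for a reference value.
- f = 0.80: at most 0.0159 × 0.223 = 0.0035, about 0.4%.
- f = 0.50: 0.0105 × 0.693 = 0.0073 to 0.0159 × 0.693 = 0.0110, so 0.7 to 1.1%.
- f = 0.25: 1.4 to 2.2%.

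**Widening of the limits by one cut second reference value.** Protocol 4.2.2 gives a CV of 33.4% for AUC, so s² = ln(1 + 0.334²) = 0.1058. The expected addition is (ln f)² × (1 − 1/16)/(2 × 30) = (ln f)² × 0.015625. The limits are exp(∓0.760 s).

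| Share kept | s² | Limits |
|---|---|---|
| No cut | 0.1058 | 78.1–128.0% |
| 0.80 | 0.1065 | 78.0–128.2% |
| 0.50 | 0.1133 | 77.4–129.1% |
| 0.25 | 0.1358 | 75.6–132.3% |

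**Probability of concluding bioequivalence, cut value kept against left out.** This was simulated with a within-subject CV of 33.4% for both products and the plan's full decision rule.
- True ratio 1.00: a change of at most about 1 point in every case.
- True ratio 0.95 (95% left out): with half kept, 97% for a second-reference cut and 93–94% for a test cut.
- True ratio 0.90 (78% left out): with half kept, 84–85% and 72–74%; with a quarter kept, 91–93% and 63–67%.
- True ratio 1.11 (78–79% left out): with half kept, 76–77% and 82–83%; with a quarter kept, a period 2 reference cut lowers it by 14 points.
- With 80% or more kept: at most about 2 points at any of these ratios.

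**The case for a change.** The strongest case for a change is that the text, taken at its word, gives the wrong answer. *Valid* is not defined. *Evaluable* is explained only as nonmissing, which a cut AUC0-t satisfies. A condition on completed periods does not say that an incomplete period is dropped. A review without treatment allocation limits bias but supplies no criterion, so two careful analysts could build different primary datasets. The planned outlier analysis changes only the acceptance range, not the ANOVA estimate. Near the scaling threshold the effect on CV_WR can be qualitative: from an assumed 28%, one second reference value cut to 40% gives an expected CV_WR of 30.4%, which crosses 30%.

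The absence of a written completeness criterion stands, and it extends to Cmax if sampling stops before the peak. The step from there to a flawed analysis does not. Section 9 is a general statement for all data types, and the PK rules in sections 8 and 16 sit alongside it. A participant who leaves before the last sample has not, on an ordinary reading, completed that period, so the cut second reference value is not evaluable for CV_WR. A profile ended by withdrawal also fits the SAP 8.1 and 8.2 grounds for exclusion, and the flagging of excluded parameters shows that dropping a single period is foreseen. Under protocol 7.2, samples are destroyed when consent is withdrawn, so unassayed samples from that period would often yield no AUC at all. The R1-against-R2 outlier check is aimed at just this kind of inflated CV_WR: at a true ratio of 0.90, removing the cut participant from CV_WR brings the probability from 92% to 85% with a quarter kept, and from 85% to 83% with half kept.

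Two neighbouring matters are separate from this one: the one-word difference between protocol 9.3 and SAP 8.2 on study periods, and how PK data from a period with vomiting are used (protocol 5.2 and 7.2 against SAP 8.1).

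**Conclusion.** No change follows. This is a missing detail that analysts would fill sensibly: a profile that stops because the participant left would be set aside for that period at the data review, on grounds the plan already states. A written cut-off hour would be tidier, but the sponsor would have to choose it, and it would decide a case that may never arise.

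The size supports this. The effect is zero if nobody withdraws during the 12 h of sampling. One such event among 32, with half the AUC kept, moves the ratio by about 1% at most and the expected limits from 78.1–128.0% to 77.4–129.1%. At a true ratio of 1.00 the chance of success is essentially unchanged. Changes of about 15 points need three things together: a very early stop after period 1, a true ratio near 0.90 or 1.11, and a review that leaves the value in.

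These figures rest on a one-compartment profile with tmax of 1.5 to 3.5 h, equal within-subject CVs of 33.4%, 16 participants per sequence and a single event.
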